**Duration of Treatment and Follow-up:**

The duration of the Treatment Period is 52 weeks. Subjects will participate in a Safety Follow-up Visit 4 weeks after the last dose of fipaxalparant (HZN-825).

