16. Blood samples will be collected for serum and plasma biomarkers prior to dosing on Day [REDACTED] as well as at the [REDACTED] Visit.
17. Adverse events occurring or worsening after the first dose of fipaxalparant (HZN-825) on Day 1 through the Safety Follow-up Visit will be considered treatment-emergent adverse events for this trial. All adverse events that occur from the signing of informed consent through the Safety Follow-up Visit will be recorded. The subject should be assessed for the development of new onset of scleroderma renal crisis, new onset of left ventricular failure, new onset of pulmonary arterial hypertension or right heart catheterization requiring treatment, gastrointestinal dysmotility requiring enteral (tube feeding) or parenteral nutrition or digital ischemia with gangrene, amputation or hospitalization requiring treatment.
18. Includes recording of herb/supplement use. See [Table 9.1](#) for restrictions regarding medications.

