## **4.2 Study Treatments**

The dose regimen for all subjects will be HZN-825 300 mg twice every day for 52 weeks. Subjects will take 2 HZN-825 150 mg tablets orally in the morning and evening with a meal. Subjects will participate in a Safety Follow-up Visit 4 weeks after the last dose of HZN-825.

The treatment group will be based on randomized treatment in previous HZNP-HZN-825-301 trial and denoted as QD/BID (HZN-825 300mg QD/HZN-825 300mg BID), BID/BID (HZN-825 300mg BID/HZN-825 300mg BID), and PLC/BID (Placebo/HZN-825 300mg BID) accordingly.

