## **10.3 Adverse Events**

### **10.3.1 Treatment-Emergent Adverse Events.**

Treatment-emergent adverse events (TEAEs) are defined as any AEs with an onset date on or after the trial drug start date and time (if known) and no later than 28 days after permanent discontinuation of trial drug.

Refer to the table, listing, and figure shell document for determination of TEAE status in adverse events that are missing critical AE date start and stop information. All TEAEs will be evaluated for both treatment periods (start from first dose at HZNP-HZN-825-301 and HZNP-HZN-825-302 to the end of HZNP-HZN-825-302). Imputed dates are only used for classification of TEAEs.

Prior AEs are defined as any AE with a start date prior to the date of first dose of study treatment. Prior AEs will not be summarized, but will be included in listings.

Follow-up AEs are defined as any AE occurring > 28 days after permanent discontinuation of trial drug for subjects who prematurely discontinue the study medication prior to 52 weeks (i.e. 392 days after first trial drug intake). Follow-up AEs will be identified in the listings as such. Related SAEs will be followed up until resolved or until the event stabilizes and the overall clinical outcome has been ascertained.

The Verbatim terms in the eCRFs will be mapped to preferred terms (PTs) and system organ classes (SOCs) using the current version of MedDRA. Adverse events will be graded for

severity using the Rheumatology Common Toxicity Criteria (RCTC) v2.0 [[Woodworth et al., 2007](#)].

For summaries by SOC, PT, and maximum severity, a subject will only be counted once for each SOC based on the maximum severity level reported for that SOC and once for each unique PT within that SOC level at the maximum intensity level reported for that PT.

For summaries by SOC and PT only, a subject will be counted at most once at the SOC level and at most once at each unique PT within the SOC level. Summaries presenting the frequency of TEAEs by SOC and PT will be ordered alphabetically by SOC and then, within a SOC, alphabetically by PT.

Event Adjusted Incidence Rate (EAIR) is defined as number of subjects with events / total subject-years. Subject-years for each subject will be calculated as (date of first event occurred – first dose date +1)/365.25. For subjects without an event, subject-years for each subject = (last day in study – first dose date +1)/365.25.

EAIR will be summarized by SOC and PT as needed for TEAE.

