17. Adverse events occurring or worsening after the first dose of HZN-825 on Day 1 through the Safety Follow-up Visit will be considered treatment-emergent adverse events for this trial. All adverse events that occur from the signing of informed consent through the Safety Follow-up Visit will be recorded. The subject should be assessed for the development of new onset of scleroderma renal crisis, new onset of left ventricular failure, new onset of pulmonary arterial

hypertension or right heart catheterization requiring treatment, gastrointestinal dysmotility requiring enteral (tube feeding) or parenteral nutrition or digital ischemia with gangrene, amputation or hospitalization requiring treatment.

18. Includes recording of herb/supplement use. See Table 9.1 for restrictions regarding medications

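### The follow-up AE definition in SAP 10.3.1 equates 52 weeks with 392 days and covers early stoppers only, so completers' late events have no category or the wrong one, depending on the reading

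*SAP*

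**What the plan says.** SAP 10.3.1 sorts AEs by onset into three categories.

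- Prior AEs start before first dose.
- TEAEs start on or after first dose and "no later than 28 days after permanent discontinuation of trial drug".
- The third category reads "Follow-up AEs are defined as any AE occurring > 28 days after permanent discontinuation of trial drug", limited to events "for subjects who prematurely discontinue the study medication prior to 52 weeks". The SAP gives the cut-off as "prior to 52 weeks (i.e. 392 days after first trial drug intake".

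The same section plans tables by system organ class and preferred term for follow-up AEs and serious follow-up AEs, next to those for TEAEs and treatment-emergent SAEs. It also plans an overall summary that includes every death, and listings of all AEs and of SAEs.

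On timing, the protocol synopsis states "The duration of the Treatment Period is 52 weeks". SAP 4.2 adds, with no restriction to early stoppers, "Subjects will participate in a Safety Follow-up Visit 4 weeks after the last dose of HZN-825". The schedule of assessments (Protocol 2.1, and the version 2.2 schedule reproduced in SAP 14) gives that visit a window of ±14 days and has AEs recorded up to it.

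The end of the TEAE period is stated in two ways. Footnote 17 of both schedules says that events after first dose "through the Safety Follow-up Visit will be considered treatment-emergent adverse events for this trial". Protocol 9.5.3.1.2 ends the period 4 weeks after last dose, and the primary safety objective (Protocol 8.1, SAP 4.1.1) uses the same 4 weeks.

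**The concern.** The three categories should between them hold every recorded AE, and each AE should fall in the same place whoever programs the tables. Two features of the follow-up AE definition prevent this. It excludes subjects who complete treatment, although their AEs are recorded up to a visit that may fall after day 28. And the day count in its cut-off is not 52 weeks.

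At stake is the content of the follow-up AE and serious follow-up AE tables. A completer's non-fatal SAE with onset on, say, day 35 after last dose could be missing from both the treatment-emergent and the follow-up tables, or could be tabulated as an event in a subject who stopped early. Safety and tolerability form one of the two primary objectives, so these tables matter even though the trial is descriptive.

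**Working it through.** **Inputs.** Treatment of 52 weeks (protocol synopsis; SAP 4.2). Stated day equivalent 392 and TEAE limit of 28 days after stopping (SAP 10.3.1). Safety Follow-up Visit 4 weeks ±14 days after last dose (Protocol 2.1; SAP 14). Week 52 window ±5 days in SAP 14 (protocol version 2.2) and ±7 days in Protocol 2.1 (version 3.0). Days are counted from first dose; shifting by one to match the SAP study-day convention changes nothing below.

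**The plan's own figure.** 52 × 7 = 364 days, so 392 is not reproduced. 392 / 7 = 56.0 weeks, and 364 + 28 = 392. The figure equals treatment plus the 28-day follow-up, but the sentence equates it with 52 weeks.

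**When AEs are recorded after last dose.** The visit falls between 28 − 14 = 14 and 28 + 14 = 42 days after last dose. Recording can therefore run past the TEAE limit by up to 42 − 28 = 14 days (days 29 to 42).

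**Last dose of an on-schedule completer.** With ±5 days: 359 to 369. With ±7 days: 357 to 371. All lie below 392, by 23 to 33 days (±5) or 21 to 35 days (±7).

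**Classifying an AE with onset 29 to 42 days after last dose:**

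| Subject | Early stopping from completion status | Last dose before day 392 | Last dose before day 364 |
|---|---|---|---|
| Stops at day 200 | follow-up AE | follow-up AE | follow-up AE |
| Completer, last dose day 357 to 363 | no category | follow-up AE, as an early stopper | follow-up AE, as an early stopper |
| Completer, last dose day 364 to 371 | no category | follow-up AE, as an early stopper | no category |

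An AE with onset at 28 days or less is a TEAE in every cell. For the true early stopper the periods join under all readings.

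**A related ambiguity.** SAP 10.3.1 evaluates TEAEs for two periods, one starting at first dose in HZNP-HZN-825-301, and does not say which first intake the 392 days run from. Counted from the earlier trial, assuming 52 weeks there, 392 days is 56 − 52 = Week 4 of this trial.

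**The case against.** The strongest reply is that the operative words are about subjects who prematurely discontinue. Protocol 9.3.3.1 gives treatment completion its own eCRF category, and SAP 8.1 reports premature discontinuation with reasons. A sensible programmer would use that record, and 392 is probably a misplaced end-of-follow-up day. This makes the mislabelling of completers less likely, but it leads straight to the other outcome, in which their late events have no category.

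A reader might infer several stronger things that the documents do not support.

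- **That both faults occur together.** They are alternatives. Under the 392-day test, completers' late events do reach the follow-up tables, though as events of early stoppers.
- **That events are lost from all reporting.** All deaths enter the overall summary, and all AEs and SAEs recorded in the trial are listed. The gap concerns non-fatal events in completers.
- **That a third of the post-treatment period is uncovered (14 / 42 = 33%).** That needs a visit on the last day of its window. At the nominal 4 weeks or earlier, the gap in scheduled collection is zero.
- **That the 28-day TEAE limit is itself wrong because of footnote 17.** The limit agrees with Protocol 9.5.3.1.2, with the primary safety objective and with the liver summary in SAP 10.3.3.2. SAP 14 is a reproduced protocol schedule, not a separate analysis rule. The conflict lies between the protocol's footnote and its own body text.

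It is also true that no formal test or efficacy endpoint depends on these labels.

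**Conclusion.** The point holds in a limited form. The day count is wrong by 392 − 364 = 28 days. The definition leaves completers' events after day 28 either without a category (early stopping judged by completion status) or attributed to premature discontinuers (392 days used as the test). Because the SAP tabulates these categories, this is a working rule with a reading-dependent result, not just a slip of the pen.

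The size is modest. Under scheduled collection at most 14 days per completer are affected, and only when the Safety Follow-up Visit is held after day 28. A related SAE reported after the trial under Protocol 9.5.3.1.5 could fall later still, if it reaches the analysis data; the protocol places such reports in the safety database. Neither document gives an expected number of events, so none is estimated. The conclusion assumes that AEs are recorded up to the visit, as both schedules say, and that the visit can fall anywhere in its window.

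**What to change.** In SAP 10.3.1:

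1. Keep the TEAE limit at 28 days after last dose.
2. Define follow-up AEs as any AE with onset more than 28 days after last dose, in any subject.
3. Delete the 392 days. If early stoppers are to be shown separately, identify them from the treatment disposition record. Simply substituting 364 would still mislabel completers whose last dose falls on days 357 to 363, early in the Week 52 window.

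Separately, footnote 17 (Protocol 2.1 and the schedule in SAP 14) and Protocol 9.5.3.1.2 must be reconciled so that the TEAE period has one stated end. Extending TEAEs to the visit would be the less attractive way to do this: it would depart from the primary safety objective and the liver summary window, and the length of the TEAE period would then vary with visit scheduling.

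The cost is a few sentences before database lock and a few more events in the follow-up AE tables. No data collection changes.

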### 4 Study Design

[figure not shown]
This is an open-label, repeat-dose, multicenter extension trial of HZNP-HZN-825-301.

Subjects who complete the double-blind Treatment Period (Week 52) in Trial HZNP-HZN-825-301 will be eligible to enter this 52-week extension trial. Subjects who enter this extension trial will complete the Week 52 Visit activities in HZNP-HZN-825-301 and will not complete the Safety Follow-up Visit 4 weeks after the last dose of trial drug in HZNP-HZN-825-301.

On Day 1 (Week 52 Visit of HZNP-HZN-825-301), subjects will receive their first dose of HZN-825 in this extension trial at the clinic and will participate in trial visits at Week 4 and every 6 weeks thereafter until Week 52. The Week 52 Visit activities in HZNP-HZN-825-301 will serve as Trial Baseline for this extension trial.

If a subject prematurely discontinues trial drug, he/she will be asked to remain in the trial, participating in the scheduled trial visits through Week 52. If a subject prematurely discontinues trial drug and does not wish to continue in the trial, he/she will return for a clinic visit and undergo the Week 52 assessments. Subjects will participate in a Safety Follow-up Visit 4 weeks after the last dose of HZN-825.

An overview of the trial design is presented in Figure 1.

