Events for which the investigator did not record relationship to trial drug will be considered related to trial drug for summary purposes. However, by-subject data listings will show the relationship as missing. No imputation will be done in case of missing study treatment relationship for non-treatment emergent AEs.

The severity grade of events for which the investigator did not record severity will be categorized as “missing” for tabular summaries and data listings. The missing category will be listed last in summary presentation.

Treatment-emergent AEs will be summarized based on the Safety Analysis Set.

Summaries of the following types will be presented:

The number and percentage of subjects who experienced at least 1 TEAE will be provided and summarized by SOC, PT, and treatment group.

The following AEs summaries will be provided by SOC, PT, and treatment group. AE summaries followed by an asterisk(\*) will include the number of events and the corresponding incidence of events per PYE.:

- All TEAEs by maximum severity
- All treatment-emergent SAEs\*
- All treatment-related TEAEs\*
- All treatment-related TEAEs by maximum severity
- All treatment-related treatment-emergent SAEs
- All TEAEs meeting CRISS criteria
- All TEAEs leading to permanent withdrawal of any trial drug
- All TEAEs leading to death (ie, outcome of death)
- All follow-up adverse events
- All serious follow-up adverse events
- Subject incidence of AESIs: [REDACTED]

A brief, high-level summary of AEs described above will be provided by treatment group for the study treatment period and by the number and percentage of subjects who experienced the above AEs. All deaths observed in the trial will also be included in this summary. For the overall summary, the category of “TEAEs by maximum severity” described above will be replaced by AEs with severity > Grade 3.

The frequency of TEAEs occurring in > 5% of subjects in any treatment group will be summarized by treatment, primary SOC, and preferred term. A similar summary will be created for serious TEAEs occurring in > 3% of subjects in any treatment group by primary SOC and preferred term.

An adverse event plot will be created with AE incidences and risk differences (with corresponding exact 95% confidence interval) plotted together for the adverse events occurring in >5% of subjects in any treatment group. A similar plot will be created for SAEs occurring in > 3% of subjects in any treatment group.

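### SAP 10.3.1: the TEAE incidence rate (EAIR) counts event-free time after the TEAE window has closed, so it can read too low and never too high

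*SAP*

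**What the plan says.** SAP 10.3.1 sets these rules:

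- A TEAE starts on or after first dose and "no later than 28 days after permanent discontinuation of trial drug".
- EAIR is the number of subjects with events divided by total subject-years. Its scope is: "EAIR will be summarized by SOC and PT as needed for TEAE".
- A subject with an event contributes time to the first event. For the rest: "For subjects without an event, subject-years for each subject = (last day in study" minus first dose date, plus 1, over 365.25. No cap is given at the end of the TEAE window.
- Later events form their own class: "Follow-up AEs are defined as any AE occurring > 28 days after permanent discontinuation of trial drug", and only "for subjects who prematurely discontinue the study medication prior to 52 weeks". A parenthesis then equates 52 weeks with 392 days after first intake.
- Two periods are planned: "All TEAEs will be evaluated for both treatment periods (start from first dose at HZNP-HZN-825-301 and HZNP-HZN-825-302" to the end of the extension).
- Some summaries, marked by an asterisk, "will include the number of events and the corresponding incidence of events per PYE". The asterisk is on treatment-emergent SAEs and treatment-related TEAEs only.

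SAP section 4 says of a subject who stops drug that "he/she will be asked to remain in the trial, participating in the scheduled trial visits through Week 52"; Protocol 9.3.3 says the same. Protocol 9.6.4 asks for AE rates per patient-year of follow-up during dosing.

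**The concern.** A rate is interpretable when an event occurring at any moment of the counted person-time would have been counted. Here that fails for anyone who stops drug early and stays. From day 29 after stopping until the last day in study, the subject accrues event-free time, but an event in that time is a follow-up AE and not a TEAE.

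Safety is a primary objective, and EAIR is the only time-adjusted rate that the SAP plans for all TEAEs. It is meant to correct for unequal follow-up. As written, it understates the rate by an amount that depends on how many stop, how early, and how many stay.

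**Working it through.** The documents state no EAIR value, stopping rate or retention rate, so there is no planned figure to reproduce. The direction follows from the text; the size needs assumptions.

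**Direction.** Compare the SAP rate with one whose event-free time ends with the TEAE window. The numerators are identical. Each subject's SAP time is equal or longer. The SAP rate is therefore equal or lower.

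**One subject.** A subject stops at Week 12 (day 84), stays to Week 52 (day 364) and has no TEAE. SAP time is 364/365.25 = 0.997 years. Time in which a TEAE could count is (84 + 28)/365.25 = 0.307 years. The excess is 252 days, or 0.69 years.

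**Population model (assumed).** The first-event hazard λ is constant. Completers are at risk and in study to Week 56. A fraction q stops at T, uniform over 0 to 52 weeks, with the TEAE window ending at T + 4. A fraction s of stoppers stays to the later of Week 52 and T + 4; the others leave at T + 4.

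For window length W and last day in study L, in years:

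- P(event) = 1 − exp(−λW)
- Matched time = (1 − exp(−λW))/λ, so the matched rate equals λ
- SAP time = matched time + exp(−λW)(L − W)
- Percent low = 1 − matched time/SAP time, averaged over subjects

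With λ = 0.30 per year, q = 30% and all staying, counted from first extension dose, the event proportion is 0.2393. Matched time is 0.7976 years per subject and SAP time is 0.9114. The rates are 0.2393/0.7976 = 0.300 and 0.2393/0.9114 = 0.2625, which is 12.5% low.

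| Stoppers who stay | 10% stop | 20% stop | 30% stop |
|---|---|---|---|
| All | 4.1% low | 8.3% low | 12.5% low |
| Half | 2.1% | 4.3% | 6.7% |
| A quarter | 1.1% | 2.2% | 3.4% |
| None | 0 | 0 | 0 |

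If EAIR is also run from the first dose in the parent trial (52 weeks added at the same hazard), the all-stay row becomes 1.8, 3.7 and 5.5%. The SAP's two-period sentence implies this version, but the EAIR formula does not say which first dose date it uses.

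**Sensitivity.** With 30% stopping and all staying, from first extension dose, the result barely moves with the event rate: 12.2% low at 0.1 per year and 13.2% at 1.0. It moves more with when subjects stop. At 0.10 per year, if all stoppers stop at day 84 it is 20.0% low; at day 273 it is 4.8% low.

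**Window end.** SAP 10.3.1 (28 days) and Protocol 9.5.3.1.2 (4 weeks after last dose) agree. Footnote 17 to the schedule, in Protocol 2.1 and in the SAP appendix, runs to the Safety Follow-up Visit. That visit is at 4 weeks ± 14 days, so day 14 to day 42. Footnote 17 also counts worsening, whereas SAP 10.3.1 uses onset date only.

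**392 days.** 52 × 7 = 364, while 392 = 364 + 28. The two thresholds defining follow-up AEs differ by 28 days.

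**Severity row.** In its high-level AE overview, SAP 10.3.1 uses AEs above Grade 3. On the 1 to 4 scale of Protocol 9.5.3.1.3 that is Grade 4 only. Protocol 9.6.4 summarizes TEAEs of Grade 3 and above.

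**The case against.** The best defence is about weight. EAIR is produced only as needed, SAP section 9 plans no formal analyses in this single-arm trial, and the shortfall is a few percent or less unless many subjects stop and most of them stay. All of that stands and limits the severity. It does not rescue the formula: whether to produce the rate is optional, but its definition is not. Nor can it be defended as a whole-study rate, because that would require follow-up AEs in the numerator.

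Stronger readings are tempting, and the documents do not support them:

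- **That the SAP's window departs from the protocol's.** Protocol 9.5.3.1.2 agrees with the SAP's 28 days. The conflict is between those two sections and footnote 17, so it also lies inside the protocol.
- **That a completer's AE on days 29 to 42 is certainly unclassified.** This holds if a completer's last dose counts as permanent discontinuation and 52 weeks means 364 days. If 392 days is the operative threshold, it could be a follow-up AE. If permanent discontinuation means early stopping only, completers have no day-28 cap.
- **That adding the per-PYE asterisk to all TEAEs would cure the problem.** The SAP abbreviates PYE as person-years of exposure but gives no formula. If it means dosing time as in SAP 10.1, TEAEs still count for 28 more days. With no stoppers and a constant event rate, the result reads 56/52 − 1 = 7.7% high. Under the stopping model above, mean window over mean dosing time at 30% stopping is (0.7 × 56 + 0.3 × 30)/(0.7 × 52 + 0.3 × 26) = 48.2/44.2, or 9.0% high.
- **That comparisons between prior-treatment groups are distorted in a known direction.** No stopping or retention figures by group are given.
- **That Grade 3 events go unreported.** They remain visible in the SOC/PT table by maximum severity.

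**Conclusion.** The denominator rule is wrong as written and should be fixed. EAIR for TEAEs can be too low and cannot be too high. From first extension dose, the assumed scenarios in the table range from 0 to 12.5% low, with smaller values if the parent trial's 52 weeks are included. These figures rest on a constant hazard, uniform stopping and the assumed retention; the direction rests on the SAP text alone.

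Crude counts and percentages are untouched, and premature discontinuers' later events appear in the follow-up AE tables. The window-end, 392-day and severity-row points are secondary clarifications. Comparisons with the protocol use the supplied Version 3.0, whereas the SAP cites Version 2.2; the core point and the footnote 17 conflict both arise within the SAP itself.

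**What to change.** **EAIR.** For subjects without an event, set subject-years = (min(last day in study, last dose date + 28 days) − first dose date + 1)/365.25. State which first dose date applies to each analysis period, and keep the cap equal to whatever TEAE window end is adopted.

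**Dosing-time rate.** If the Protocol 9.6.4 rate is added for all TEAEs, match its two parts: either events on dosing days over dosing time, or TEAEs over dosing time plus 28 days. Define PYE. Do not simply extend the asterisk.

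**TEAE definition.** Reconcile SAP 10.3.1 and Protocol 9.5.3.1.2 with footnote 17 in both documents. Decide whether the window ends at 28 days or at the Safety Follow-up Visit, and whether worsening counts. Correct the 52-week/392-day text and say which class holds a completer's AE on days 29 to 42.

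**Overview row.** Change it to TEAEs of Grade 3 or higher.

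The cost is a few SAP sentences, a matching footnote correction and minor programming. The last treatment day is already derived for exposure in SAP 10.1, and no new data are needed. Reported EAIR would be equal or higher.
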